## Abstract

**Abstract:** Gastric cancer (GC) is the fifth with the highest incidence and mortality worldwide (1). It is a multifactorial and heterogeneous disease, where both environmental and genetic factors are involved. Three hereditary syndromes primarily affect the stomach: Hereditary Diffuse Gastric Cancer (HDGC), Gastric Adenocarcinoma and Stomach Proximal Polyposis (GAPPS), and Familial Intestinal Gastric Cancer (FIGC) (2), but in addition to these, many other syndromes and genetic mutations are associated with an increased risk of GC (3–5). As GC is a neoplasm with numerous somatic and hereditary mutations involved in its carcinogenesis, the use of the Multigene Germline Panel Test (MGPT) may be crucial, as it allows the analysis of hereditary mutations in a significant number of genes simultaneously (6,7). This observational, retrospective study aims to quantify and characterise the pathogenic variants (PVs) found in the MGPT of GC patients in Alto Alentejo (Portugal).

## Introduction

**Background/ Rationale** According to data from the Global Cancer Observatory, gastric cancer (GC) ranks fifth in terms of incidence and mortality worldwide (1).

It is a multifactorial and heterogeneous disease involving both environmental and genetic factors. Although the majority of cases are sporadic, caused by environmental exposures, up to 20% of patients have a familial aggregation and of these, 3 to 5% are classified as hereditary with an identified mutation (8,9).

Three hereditary syndromes primarily affect the stomach: Hereditary Diffuse Gastric Cancer (HDGC); Gastric Adenocarcinoma and Stomach Proximal Polyposis (GAPPS); and Familial Intestinal Gastric Cancer (FIGC) (2). HDGC is an autosomal dominant syndrome, predominantly caused by germline mutations in the *CDH1* gene, which encodes the e-cadherin protein with important functions in cell aggregation, and is characterised by a high risk of early-onset diffuse GC and invasive lobular breast cancer (10). GAPPS is caused by germline mutations in *APC* promoter 1B and is characterised by the presence of fundic gland polyposis with focal dysplasia and intestinal or mixed adenocarcinoma at the level of the gastric fundus and sparing the antrum (4,11). Finally, FIGC is an autosomal dominant syndrome, still poorly characterized genetically, which is associated with an increased risk of intestinal GC (10).

Other genetic syndromes are also associated with an increased risk of GC. Some of the genes involved include *MLH1*, *MSH2*, *MSH6*, and *PMS2* (Lynch Syndrome - LS), *TP53* (Li-Fraumeni Syndrome), *APC* (PAF and ADC / proximal polyposis of the stomach) and *MUTYH* (Polyposis Associated MUTYH), *BMPR1A* and *SMAD4* (Juvenile Polyposis Syndrome), *STK11* (Peutz-Jegher Syndrome) and *PTEN* (Cowden Syndrome) (3–5).

As GC is a neoplasm with numerous somatic and hereditary mutations involved in its carcinogenesis, the use of MGPT can be crucial, as it performs the analysis of hereditary mutations in a significant number of genes simultaneously (depending on the genes included in the panel) (6,7). In addition to the described mutations, MGPT has allowed the identification of new genetic mutations associated with GC risk, including in the *BRCA 1/2*, *PALB2*, *ATM* and *RAD51C* genes (typically associated with hereditary breast and ovarian cancer), *MAP3K6*,

MYD88, among others (9,12–17). However, the use of MGPT, especially in unselected GC patients, is not without risks, such as the unexpected detection of PV in genes not strictly associated with the phenotype (secondary findings) or, more commonly, the high rate of variants of unknown significance (VUS), which can raise important questions regarding the uncertainty of how to approach these patients (18). Therefore, some studies advocate that MGPT or single gene testing (SGT) should be offered only to selected patients, especially those with suspected HDCG (5,19–21). On the other hand, the evidence of many other germline mutations associated with GC and the lack of genetic characterisation of FIGC justifies the growing interest in performing MGPT in unselected patients with GC (10,18,22,23). Although these studies suggest a benefit in the use of MGPT in unselected patients with GC, this test is not yet widely used.

In Portugal, the incidence and mortality rates of GC have been increasing over the last few decades. It is therefore important to better understand the genetic characteristics of GC in this country in order to develop better strategies for managing this disease.

## Objectives

The **main objective** of this research is to quantify and characterize the PV found in MGPT of GC patients in Alto Alentejo (Portugal).

The **specific objectives** are:

- Determine the global rate of PVs in GC patients of Alto Alentejo;
- Determine which PVs are most common in our GC population;
- Correlate the PVs found with clinical factors: Age at diagnosis; Sex; Weight; Height; Presence of other diseases (Diabetes; Arterial Hypertension; Dyslipidaemia; Stroke; Heart attack); Date of diagnosis; Stage at diagnosis; Histologic subtype; Surgery for GC; Personal history of other cancers; Familial history of GC and other cancers;
- Correlate the PVs found with prognostic factors: 12-month survival rate; mortality.

## Methods

### Study design

Observational, retrospective study

Despite this design, there was uniformity in the data recorded for each participant who agreed to be submitted to MGPT, minimizing the variability between records or the missing clinical data.

### Setting

This study takes place at the Unidade Local de Saúde do Alto Alentejo (ULSAALE). The MGPT was always performed in the same laboratory (Germano de Sousa – Centro de Genética Laboratorial) using peripheral blood samples from patients with GC.

Two types of MGPT were used:

- MGPT 4005 (15 genes): APC, ATM, BLM, BMPR1A, CDH1, CTNNA1, EPCAM, MLH1, MSH2, MSH6, PMS2, PTEN, SMAD4, STK11/TP53.
- MGPT 4013 (30 genes): ATM, BARD1, BLM, BRCA1, BRCA2, BRIP1, CDH1, CHEK2, EPCAM, FANCC, MLH1, MRE11A, MSH2, MSH6, MUTYH,

NBN, NF1, PALB2, PMS2, PTEN, RAD50, RAD51C, RAD51D, RECQL4, RINT1, SLX4, SMARCA4, STK11, TP53, XRCC2.

The majority of patients with GC were tested with MGPT 4005. Patients with neoplasms other than GC or with a family history of other neoplasms were tested with MGPT 4013. The decision to perform MGPT and the choice of panel type were made in multidisciplinary consultation.

The recruitment process takes place between January 2023 and December 2024. All data will be collected and entered in a database until September 2025

The manuscript for publication will be written between October and November 2025.

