#### **Data sources**

The variables related to the patient's clinical history and personal data will be collected through a questionnaire administered during a personal interview and supplemented by consultation of each patient's digital medical record in order to obtain more detailed information on the variables characterising the disease and the results of the MGPT.

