#### **Bias**

Efforts to address potential sources of bias:

**Clear Inclusion and Exclusion Criteria:** The inclusion criteria are clear to select patients that are representative of the target population (patients with gastric adenocarcinoma) and that there is no bias in participant selection.

**Control of Confounding Factors:** There are some confounding factors that may influence the study results, such as age, sex, Weight; Height; Body mass index; **Presence of other diseases:** Diabetes; Arterial Hypertension; Dyslipidaemia; Stroke; Heart attack). This will be achieved through appropriate statistical techniques or data stratification during analysis.

**Uniformity in data records:** There was uniformity in the data recorded for each participant who agreed to be submitted to MGPT, minimizing the variability between records or the missing clinical data.

**Consistent and Accurate Data Collection:** This will be achieved through adequate training of interviewers or data collection personnel and the use of standardized data collection protocols.

**Blind Data Assessment:** After collection, the data will be pseudo-anonymized so that the researcher who analyses the data will not have access to the patient's identifying data.

**Time-Sensitive Analysis:** Data analysis takes into account the timing of data collection relative to relevant clinical events.

**Sensitivity Analysis:** It will be performed a sensitivity analyses to assess the robustness of the results across different results of MGPT and clinical factors.

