#### **Quantitative variables**

For quantitative variables we will do the descriptive statistics analyses with mean, mode, median, standard deviation, interquartile variation, maximum and minimum.

Subgroup analysis will be carried out, for each quantitative and qualitative variable, dividing patients who have positive or negative MGPT. We will analyse the effect measures of the difference between the two groups, with confidence interval (IC) 95%, and if possible, inferential statistical analysis will be conducted.

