**Table 2 - Variables / Measurements**

Type of Variable	Name of Variable	Measurements
MGPT Outcomes variables	MGPT	positive (1) or negative (0)
	PV	integer number
	Likely pathogenic variables (LP)	integer number
	Name of genes with PV	descriptive
	PV in each gene	integer number
	VUS	integer number
Potential confounders variables	Age at diagnosis	Years
	Sex	Female(1)/Male(0)
	Weight	Kg
	Height	cm
	Body mass index	Kg/m 

	Presence of other diseases: Diabetes; Arterial Hypertension; Dyslipidaemia; Stroke; Heart attack);	Yes(1)/No(0) for each disease
	Stage at diagnosis (AJCC staging system);	0, I, IIa, IIb, III, IVa, IVb
	Histologic subtype;	Intestinal (1); Diffuse (2); Mixed (3)
"Exposures" variables	Personal history of other cancers	Yes (1)/No (0)
	Types of other cancer in GC patient	descriptive
	Familial history of GC	Yes (1)/No (0)
	Age of onset of each familial case of GC	integer number
	Familial history of other cancers (specifying)	descriptive
	Age of onset of each familial case of other cancers	Years
Prognostic related variables	12-months survival	Yes (1)/No(0)
	Death due to GC	Yes (1)/No(0)
	Date of death	mm/yyyy
Other variables:	Date of diagnosis	mm/yyyy
	Localization of tumor	Cardia / Fundos / Body / Antrum/pyloro
	Time since diagnosis until the current moment	months
	Surgery for GC	Yes (1)/No (0);
	Type of surgery	Total gastrectomy (1); Subtotal gastrectomy (0)
	Date of Surgery	mm/yyyy
	Histologic staging after surgery	0, I, IIa, IIb, III, IVa, IVb
	Underwent chemotherapy	Yes (1) / No (0)
	Type of chemotherapy	descriptive

	Cycles of chemotherapy	integer number
	Positive MGPT is considered when it is found at least one PV in one gene of teste	A comparative analysis will be made between the individual characteristics and tumor characteristics of positive MGPT cases with those with negative MGPT.

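### The gene panel was chosen by personal or family history of other cancers, yet panel type is not a study variable: comparisons by that history mix association with genes tested, and gene counts have no stated denominator

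*Combined protocol and SAP*

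**What the plan says.** The Setting section of the combined protocol and SAP lists two germline panels: 4005 with 15 genes and 4013 with 30. Most patients had 4005. The rule for the other panel is "Patients with neoplasms other than GC or with a family history of other neoplasms were tested with MGPT 4013", with the choice made in multidisciplinary consultation.

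Table 2 defines the outcome without regard to panel: "Positive MGPT is considered when it is found at least one PV in one gene of teste". It also lists "PV in each gene" as an integer. Its exposure variables include personal history of other cancers and "Familial history of other cancers (specifying").

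The Objectives include correlating PVs with both histories and finding which PVs are most common. The Quantitative variables section states: "Subgroup analysis will be carried out, for each quantitative and qualitative variable, dividing patients who have positive or negative MGPT". Effect measures with 95% confidence intervals are planned, and "if possible, inferential statistical analysis will be conducted".

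Panel type is not in Table 2. The Bias section names confounders "such as age, sex, Weight; Height; Body mass index" and several comorbidities, but not panel. The Statistical methods section plans a logistic regression without naming panel. The Data sources section says the medical record will supply "more detailed information on the variables characterising the disease and the results of the MGPT".

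**The concern.** The histories that are to be compared between positive and negative patients also decided which genes were examined. A patient with another cancer, or relatives with other cancers, had 19 genes tested that the remaining patients did not, and missed four that they had. What counts as positive therefore differs by exposure. A difference in positivity by history could come wholly from panel content, or a real difference could be hidden by it.

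Two further results depend on the panel mix. A gene on one panel only was examined in part of the sample, so its raw count cannot be ranked fairly against a gene tested in everyone. The pooled PV rate has no fixed gene set, yet the Risks and Benefits section sets the study's result against a literature figure of 3-5%.

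**Working it through.** **Plan's own figures.** Reading STK11/TP53 as two genes, the printed lists contain 15 and 30 distinct genes, as stated. The sample size of 56 also reproduces if p = 0.5 is assumed: n0 = 1.96² × 0.25 / 0.05² = 384.1, and 384.1 / (1 + 383.1/65) = 55.7, rounded up to 56.

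**Overlap of the panels.**
- Shared (11): ATM, BLM, CDH1, EPCAM, MLH1, MSH2, MSH6, PMS2, PTEN, STK11, TP53.
- Only on 4005 (4): APC, BMPR1A, CTNNA1, SMAD4.
- Only on 4013 (19): among them BRCA1, BRCA2, PALB2, RAD51C, CHEK2, MUTYH.
- Total: 11 + 4 + 19 = 34, so 23 genes were tested in only part of the sample.

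**Spurious odds ratio (OR).** The documents give neither PV yields nor the panel split, so both are assumed, with no true association between history and PVs. For each panel, positive rate = 1 − (1 − shared)(1 − panel-specific). At 4% shared, 1% 4005-only and 6% 4013-only:
- 4005: 1 − 0.96 × 0.99 = 4.96%
- 4013: 1 − 0.96 × 0.94 = 9.76%

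Under the Setting rule everyone with a given history had 4013. Those without it are all the 4005 patients plus the 4013 patients who qualified through the other history. For 17 on 4013, 8 with personal history: (39 × 4.96% + 9 × 9.76%) / 48 = 5.86%, so OR = (0.0976/0.9024) / (0.0586/0.9414) = 1.74.

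| On 4013 / personal / family, of 56 | No personal history: % positive, OR | No family history: % positive, OR |
|---|---|---|
| 14 / 6 / 10 | 5.73, 1.78 | 5.38, 1.90 |
| 17 / 8 / 12 | 5.86, 1.74 | 5.51, 1.86 |
| 20 / 8 / 15 | 6.16, 1.65 | 5.55, 1.84 |
| 25 / 8 / 20 | 6.66, 1.52 | 5.63, 1.81 |

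Other assumptions, over the same four splits:

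| Shared / 4005-only / 4013-only | OR, personal | OR, family |
|---|---|---|
| 4% / 1% / 6%, 20% of patients off the rule in both directions | 1.29-1.42 | 1.43-1.47 |
| 2% / 0.5% / 8% | 2.03-2.87 | 3.00-3.38 |
| 2% / 1% / 0% | 0.70-0.75 | 0.68-0.70 |
| equal panel-specific yields | 1.00 | 1.00 |

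**False significance.** By exact enumeration of Fisher's test (two-sided 5%, n = 56, shared 4%, 4005-only 1%, 4013-only 2-8%), 1.2-4.8% of studies would be falsely significant for personal history and 1.2-10.5% for family history.

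**Adjusting for panel.** Under the rule no 4005 patient has either history, so a panel-adjusted estimate rests on the 4013 patients alone. At 4%, 1% and 6% they yield 14 × 0.0976 = 1.4 to 25 × 0.0976 = 2.4 expected positives.

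**Denominators.** Since most patients had 4005, at most 27 of 56 had 4013. Dividing a 4013-only gene's count by everyone understates its rate at least 56/27 = 2.07-fold, and more than 2-fold at any sample size. For a 4005-only gene with 14 to 25 patients on 4013, the factor is 56/42 = 1.33 to 56/31 = 1.81. Ranking can reverse: with 17 on 4013, two APC carriers outnumber one BRCA2 carrier, but the rates among those tested are 2/39 = 5.1% and 1/17 = 5.9%.

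**Pooled rate.** At 4%, 1% and 6%, a 10% share on 4013 gives 0.90 × 4.96% + 0.10 × 9.76% = 5.4%; a 49% share gives 0.51 × 4.96% + 0.49 × 9.76% = 7.3%.

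**The case against.** The best reply is that the size of the problem is unknown. The larger odds ratios come from assumed yields of 6% and 8% in the 4013-only genes, for which the documents offer no source. That stands: the documents establish the mechanism, not its magnitude or sign.

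Second, the confounder list is open-ended and generic sensitivity analyses are planned, so adjustment for panel is not excluded. It is not planned either, and no common gene set is mentioned. Under the stated rule, adjustment could not do the work. If the consultation departed from the rule, some 4005 patients would have a history and adjustment would be less empty, but the distortion persists in the illustration.

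Third, inference is only conditional and false significance is modest. That is correct. The main harm is a biased estimate, and effect measures with intervals are planned whatever is tested.

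Fourth, no section says that gene counts will be divided by all patients. True: the 2-fold figure applies only if they are. The defect is that the denominator is unspecified, and the ranking example is constructed.

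Fifth, the scope is limited. Family history of gastric cancer is not part of the panel rule, and the pooled rate is a legitimate yield of testing as practised. Both points stand.

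Last, an 11-gene comparison will be very imprecise and answers a narrower question. That is why it belongs beside the any-gene result rather than in its place.

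**Conclusion.** The concern holds. By the plan's own rule and outcome definition, a difference in positive tests by personal or family history of other cancers cannot be read as an association with that history. This conclusion needs no assumed rate; the distortion vanishes only if the two sets of panel-specific genes happen to have equal yields. With full adherence to the rule, the illustrative odds ratios run from 0.68 to 3.38 where the truth is 1; those values rest on assumed yields and splits.

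The gene ranking and the pooled rate also depend on panel mix, and the pooled rate is not directly comparable with the 3-5% benchmark. This should be fixed before analysis. Testing is complete, so the remedy lies in data capture and reporting.

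**What to change.** 1. Add panel type (4005 or 4013) to Table 2.
2. Report each gene's PV rate over the patients tested for that gene: everyone for the 11 shared genes, 4005 patients for the four genes only on that panel, 4013 patients for the other 19. Give the any-gene rate by panel. Label the pooled rate as the yield of testing as practised, not directly comparable with 3-5%.
3. For personal history and for family history of other cancers, show the comparison for a PV in the 11 shared genes beside the any-gene comparison. State that the any-gene result is affected by panel choice and must not be read as an association with history.

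The cost is one variable that should be recoverable from the laboratory report, plus analysis wording. Gene names are already collected.

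The price of step 3 is imprecision. At an assumed shared-gene rate of 2-4%, 56 patients give 56 × 0.02 = 1.1 to 56 × 0.04 = 2.2 carriers, with a chance of none of 0.98^56 = 32% to 0.96^56 = 10%. With 1 carrier among 8 with personal history and 1 among 48 without, the exact 95% interval for the odds ratio is 0.07 to 538; with 1 of 12 against 1 of 44 for family history it is 0.05 to 314. It should be presented as an estimate with a very wide interval, not as a test.

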### **Participants**

Eligibility criteria:

- Adult patients (over 18 years old) with a histologically proven diagnosis of gastric adenocarcinoma that have done MGPT between 2023 and 2024;
- Ability to understand and speak Portuguese and/or English language;
- Ability to reliably provide informed consent for inclusion in the study.

There are no matched or randomized groups.

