#### **Statistical methods**

- a) Statistical analysis will be carried out using SPSS software.
- b) In inferential statistical analysis, the normality of the distribution of quantitative variables will be determined by the Kolmogorov-Smirnov test. For variables with normal distribution, the T-sudent test will be used and for those that do not have normal distribution, the Mann-Whitney test will be performed, with the purpose of analysing the statistical significance of the difference between the groups with IC 95% (positive MGPT and negative MGPT). For qualitative variables, the statistical significance of the difference between groups, with 95% CI, will be calculated using the Chi-square test (if more than 10% of the cells in the 2x2 tables have frequencies  $\leq 5$ ) or the Exact Fisher Test.

We will later perform a multivariate analysis with logistic regression to control confounding variables.

- c) Missing data: We addressed missing data by employing multiple strategies. Firstly, we conducted a thorough examination of patterns of missingness to discern if they followed a missing completely at random, missing at random, or missing not at random pattern. Subsequently, for cases with missing data, we utilized multiple imputation techniques to impute missing values based on observed data and variables that were predictive of missingness. Additionally, we performed sensitivity analyses to assess the robustness of our findings to different assumptions regarding the missing data mechanism. Overall, these

approaches allowed us to minimize bias and maintain the integrity of our analyses in the presence of missing data.

d) To conduct sensitivity analysis for this study, we will systematically vary key parameters or assumptions within our analytical framework to assess their impact on the study outcomes. This may involve testing different statistical models, criteria for participant inclusion/exclusion, handling of missing data, or adjustments for potential confounding variables. By exploring a range of scenarios, we aim to evaluate the robustness of our findings and assess the degree to which they are influenced by specific methodological choices or assumptions. Sensitivity analysis allows us to identify the potential sources of uncertainty and to provide a more comprehensive understanding of the reliability and generalizability of our study results.

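### 12-month survival and gastric cancer death are analysed as Yes/No with no time origin, entry date or censoring rule, although patients enter only if alive for testing, consent and interview

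*Combined protocol and SAP*

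**What the plan says.** The last specific objective is "Correlate the PVs found with prognostic factors: 12-month survival rate; mortality". In Table 2 the prognostic variables are "12-months survival" and "Death due to GC", both coded Yes/No, plus month and year of death. Table 2 also lists month and year of diagnosis and "Time since diagnosis until the current moment". It lists no date of the multigene panel test (MGPT), no consent date and no date last known alive.

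Under Participants, a patient needs a "histologically proven diagnosis of gastric adenocarcinoma that have done MGPT between 2023 and 2024" and "Ability to reliably provide informed consent for inclusion in the study". Data sources adds a questionnaire given in a personal interview. No section limits the time from diagnosis to any of these steps. Setting places recruitment in January 2023 to December 2024 and has data entry end in September 2025.

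On analysis, Quantitative variables states: "Subgroup analysis will be carried out, for each quantitative and qualitative variable, dividing patients who have positive or negative MGPT". Statistical methods names Student's t, Mann-Whitney, chi-square and Fisher tests, then "We will later perform a multivariate analysis with logistic regression to control confounding variables". The Bias section says that the analysis allows for when data were collected relative to clinical events, but names no method.

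**The concern.** A Yes/No survival variable has a meaning only if the start of the clock is fixed and everyone is followed to the end of the window. The plan secures neither.

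Entry depends on having survived to testing, consent and interview. If the clock starts at diagnosis, early deaths are removed before the cohort is formed, and a patient who enters a year or more after diagnosis is a certain survivor. If it starts at the test, the latest entrants may not reach 12 months before data close. Gastric cancer death has no window at all, so its proportion depends on how long each patient happened to be followed. None of the named methods handles late entry or censoring.

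At stake are the absolute 12-month survival and death proportions that the study would report, overall and by MGPT result.

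**Working it through.** **Inputs from the documents.** Recruitment January 2023 to December 2024 (24 months) and data close September 2025 (Setting); 56 patients (Study size); Yes/No coding (Table 2).

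**Inputs assumed.** The documents give no survival rate and no delay from diagnosis to entry. I take a constant hazard and a true 12-month survival S of 50%, with a range of 40-60%.

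**The plan's own figure.** With z = 1.96, margin 0.05, population 65 and an unstated p taken as 0.5, n0 = 1.96² × 0.25 / 0.05² = 384.15 and n = 384.15 / (1 + 383.15/65) = 55.7, rounded up to 56. The figure reproduces. It is not tied to survival and is used here only for scale.

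**Origin at diagnosis.** A patient who enters d months after diagnosis is seen only if alive at d. The recorded 12-month survival is S(12)/S(d) = S^((12−d)/12) for d below 12, and 1 for d of 12 or more.

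| Entry after diagnosis | S = 40% | S = 50% | S = 60% |
|---|---|---|---|
| 1 month | 43.2% | 53.0% | 62.6% |
| 3 months | 50.3% | 59.5% | 68.2% |
| 6 months | 63.2% | 70.7% | 77.5% |
| 12 months or later | 100% | 100% | 100% |

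For delays spread evenly over 0-6 months, the rate is S divided by the mean of S(d). At S = 50% this is 0.5/0.845 = 59.2% (49.9-68.0% over the range). The error is upward whenever entry follows diagnosis. Patients diagnosed after September 2024 also lack 12 months of follow-up at the close.

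**Origin at the test.** The inflation disappears if consent and interview coincide with the test. However, tests in October, November and December 2024 have under 12 months to the close, depending on the exact dates: 3/24 = 12.5% of recruitment months, or 56 × 0.125 = 7 patients if recruitment is even. Those who die within 12 months can be coded No. Those alive at the close cannot be coded.

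Consent may also come after the test. Ethical Issues cites an approval record numbered 06/2024, while eligible tests start in 2023. Consent timing is not given, so this is only a possibility, but it is why entry should be the later of the two dates.

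**Gastric cancer death.** Potential follow-up from recruitment runs from 8-9 months (31 December 2024 to 1 or 30 September 2025) to 32-33 months (1 January 2023 to the same dates). One crude proportion mixes all of these.

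**The case against.** **Absolute survival is not the target.** The objective is to relate PVs to outcome, and the planned contrast is MGPT positive against negative. This is a fair limit. A reader might infer that the contrast itself is biased, but the documents do not show that. It would require time to testing or early mortality to differ by PV status, and nothing is reported on either. The objective does name a 12-month survival rate, so the figure for each group still needs a time base.

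**The delay may be short.** It may be: entry at one month adds about 3 points at S = 50%. But the plan neither limits nor lists the dates needed to show it.

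**Dates are already collected.** In part. For living patients, diagnosis date plus time since diagnosis implies a status date, although the current moment is undefined. The test date must be known to apply eligibility. Entry date and date last known alive are still not listed as variables.

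**Delayed entry from diagnosis is not clearly better.** A reader might infer that diagnosis must be the origin and that delayed-entry Kaplan-Meier then removes the bias. That holds only if testing time is unrelated to prognosis, and Setting says that testing was decided in multidisciplinary consultation. In simulations with 56 entrants and a true 50%, independent delays over 0-6 months give a mean of about 50% (standard error 9.4 points, against 6.6 for the simple rate). If half the patients have 30% survival and are tested in months 0-3, and half have 70% and are tested in months 3-6, the mean is about 43%. The root mean squared error is then about 12 points, against about 10 for the simple rate. This objection stands, and it is why the fix does not impose diagnosis as the origin.

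**Few carriers.** A reader might also infer that the Yes/No comparison is uninformative because carriers will be few. That is a separate question of power. It depends on a carrier rate not known for these panels, and a defined time origin would not repair it.

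**Conclusion.** The concern holds for absolute survival and for the death proportion. As written, neither candidate origin gives a usable 12-month variable: diagnosis overstates survival, and the test leaves some late survivors without a code. The general sentence on timing in the Bias section does not settle this.

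At an assumed true 50% and constant hazard, the overstatement from diagnosis is about 3, 9.5 and 21 points for entry at 1, 3 and 6 months. These are illustrations, because the documents give neither the delay nor the survival rate. The count of about 7 of 56 assumes even recruitment. The follow-up range of 8-9 to 32-33 months comes from the stated dates.

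The direction and size of any bias in the MGPT-positive versus negative comparison are undetermined. The main objective, the PV rate, is unaffected by this analysis choice. The point should be fixed before analysis, but it affects a specific objective only.

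**What to change.** 1. Add three fields to Table 2: MGPT date, consent date and date last known alive.
2. State the time origin and the data cut-off.
3. Replace the Yes/No analysis with Kaplan-Meier for all-cause death, censored at the date last known alive. Read 12-month survival from the curve with its 95% CI.
4. The simplest origin is study entry, the later of MGPT and consent. Label the result as survival after entry in tested, consenting patients.
5. If the investigators prefer diagnosis as origin, use delayed entry at that same date, or start the curve at a stated landmark and label it conditional on surviving to it. State that the estimate assumes time to testing is unrelated to prognosis.
6. List gastric cancer deaths and other deaths separately, and report survival by PV status descriptively.
7. Limit any retained Yes/No figure to patients whose chosen origin is at least 12 months before the cut-off, and label it conditional on enrolment.

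**Cost.** Revised wording and up to three date fields. The test date is already needed for eligibility; the documents do not say whether the other two are recorded. No new patients or visits are needed. Precision is lower. With diagnosis as origin, early risk sets are small: for delays spread over 0-6 months and S = 50%, about 10 of 56 at month 1 and 28 at month 3. There is then no guaranteed gain over the simple rate if testing time depends on prognosis. Origin at entry avoids this, but it answers a different question from survival after diagnosis. No version recovers patients who were never tested.
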